9.4. UNEXPECTEDNESS OF ADVERSE DRUG REACTIONS

An ADR is considered unexpected when its nature or severity is not consistent with the applicable product information (i.e., RZL-012 Investigator's Brochure).

9.5. ADVERSE EVENT REPORTING AND MONITORING REQUIREMENTS

9.5.1. General

All AEs, serious and non-serious, will be fully documented in both source documents and CRFs as described in Section 6.1.14, and each AE will be assessed in light of its clinical significance. For each AE, the investigator will provide the onset, end, intensity, treatment required, outcome, seriousness and action taken with the investigational drug. The investigator will determine the relationship to the investigational drug, i.e., causality assessment, for each AE.

Any AE occurring prior to initiation of first dose, after initiation of the first dose and or during any point throughout the study should be recorded on the AE page of the CRF. All AEs occurring until subject is terminated from the study (84 days after the injection of RZL-012), should be captured in the CRF. AEs should be recorded in the CRF using the medical

terminology found in the source documentation. Whenever possible, diagnoses should be given when signs and symptoms are due to a common etiology.

Occurrence of any serious or severe ADR must warrant clinical evaluation by the treating investigator and reported to the Sponsor/medical monitor within 24 hours.

ADRs will be followed-up until resolution, or for a maximal duration of 6 months after RZL-012 injection, whichever occurs first.

9.5.2. SAE Reporting

The PI or his designee must report to the Sponsor any SAE occurring after injection of the study treatment, regardless of their relationship to the investigational product.

Sponsor contact details for SAE reporting:

[name], [contact] or [contact].

An initial report must be faxed or emailed to [contact] [contact] within 24 hours of becoming aware of the event and must include SAE general description, start date, end date (if applicable), the reason for evaluation as a SAE, basic subject information, assessment of the relationship to the investigational product, expectedness, and study therapy information.

Follow-up information, including outcome and treatment, shall be faxed or emailed within 48 hours. Source documents to support the SAE (e.g., discharge summary, test results) shall be included in the report.

A complete SAE report must be sent to the Sponsor at the first possible date and no later than 7 calendar days after SAE end date. In addition to the information described in the initial report, this report will include AEs description and grading, treatment given (if applicable), SAE outcome, an assessment of the relationship to the investigational product, and expectedness.

SAE will be recorded on designated CRF forms in a timely manner and no later than 7 calendar days after its end date.

The PI or his designee will submit the SAE report to IRB/EC according to applicable local regulations and will update the Sponsor.

9.5.3. Expedited Reporting

Expedited reporting by PI to IRB/EC is warranted for all Suspected Unexpected Serious Adverse Reactions (SUSAR), i.e., unexpected SAEs that are considered related to study product as

defined in Sections 9.1.2, 9.1.3, and 9.4). Additional cases will be communicated by PI to IRB/EC via expedited reporting when required by local regulation.

Expedited reports will be submitted to the applicable regulatory authorities by the Sponsor or designee within the required timelines according to local regulations.

Such events must be reported within one (1) working day of the investigator becoming aware of the event. Pregnancies shall be followed for the duration of the pregnancy. It is the PI's responsibility to provide to the Sponsor follow-up information on the outcome of the pregnancy including information about any sequelae.

10. STATISTICAL CONSIDERATIONS

10.1. STUDY DESIGN AND OBJECTIVE

This study is planned as a single blind, randomized, placebo-controlled, Phase 2a, 2-cohort study for the treatment of submental fat. Eligible subjects will be randomized to receive either RZL-012 or placebo (vehicle) in each study cohort and will be monitored for safety and efficacy during 84 days of follow up.

Primary objective:

The main objective is to evaluate safety following injection of RZL-012 vs. placebo into submental fat. Skin irritancy and AEs related to the injection procedure will be evaluated for frequency, severity and duration. Specifically, tolerability and assessment of the following AEs will be monitored: bruising, pain, induration erythema and swelling/edema.

Secondary Endpoints:

Secondary endpoints will test the efficacy of RZL-012 vs. placebo according to the following measures:

- 1. Improvement of Physician's global assessment questionnaire for treatment efficacy in active vs. placebo treated subjects at Day 28, 56 and 84 following injection.
- 2. Reduction from baseline in submental fat volume as measured by MRI, in RZL-012 treated subjects vs. placebo treated subjects at Day 84 following injection.
- 3. Improvement from baseline in the self-assessment of submental fat using the Face-Q satisfaction questionnaire rating score in RZL-012 treated subjects vs. placebo treated subjects on Days 28, 56 and 84.

10.2. STUDY ENDPOINTS

10.2.1. Primary Safety Endpoints

Skin AEs will be evaluated for their frequency, severity and duration. Specifically, the assessment of the following AEs will be monitored among RZL-012 vs. placebo treated subjects: bruising, pain, induration, erythema, and swelling/edema.

10.2.2. Secondary Efficacy Endpoints

Secondary efficacy endpoints include testing of RZL-012 vs. placebo according to the following measures:

- Improvement in Physician's global assessment questionnaire for treatment efficacy assessment at Day 28, 56, and 84 following injection.
- Improvement from baseline in a quantitative measure of submental volume as measured by MRI, before and 3 months after injection.
 - Improvement from baseline in score of FACE-Q questionnaire rating subject's satisfaction on Day 28, 56, and 84 follow up visits.

10.2.3. Safety and Tolerability Endpoints

Safety endpoints include:

- Incidence of AEs and SAEs, by severity and relation to study treatment of RZL-012 vs. placebo treated subjects. AEs will be coded using MedDRA version 22 (or higher).
- Specific AEs will be closely monitored: bruising, pain, induration and swelling/ Edema and Erythema (Draize Score).
- Vital signs

10.3. SAMPLE SIZE JUSTIFICATION

A maximum of 28 evaluable subjects will be included in the study (12 cohort 1 and 16 in cohort 2) and followed for as long as 3 months.

This study is planned as a dose escalation study following randomization of 8 subjects per active dose group paradigm with the addition of a 4 subjects vehicle control group at cohort 1 (active/placebo ration of 2:1). At cohort 2, out of the 16 subjects that will be randomized, at least 4 subjects will receive placebo treatment.

Selection of sample size of 12/16 at each cohort was based on discussions with physicians and is similar in numbers to that encountered in the literature for treatments at this stage of development.

10.4. ANALYSIS SETS

10.4.1. Safety Analysis Set (SA)

The SA will consist of all enrolled subjects who received the study treatment, (exposed population), including subjects prematurely withdrawn.

All enrolled subjects receiving the study drug injection are considered evaluable for the SA set.

10.4.2. Efficacy Analysis Set (EF)

The EF will consist of all subjects from the SA analysis set without any major protocol violations measured at baseline. Subjects will be analyzed according to the treatment received.

10.4.3. Statistical Analysis of Analysis Sets

The SA analysis set will serve as the principal data analysis set for the analyses of the safety endpoints.

The EF analysis set will serve as the principal data analysis set for the analyses of the efficacy endpoints.

10.5. STATISTICAL ANALYSIS

10.5.1. General

Statistical analyses will be mainly descriptive in nature where study data will be tabulated and summarized using the mean, standard deviation or standard error. The results will be presented overall per cohort and per treatment.

AEs related to injection and Draize scores will be presented in tabular format by visit, cohort and treatment.

Improvement in Global physician's scale score pf RZL-012 treated subjects vs. placebo treated subjects by cohort and overall.

The average change from baseline in submental volume as analyzed from MRI images will be presented in a tabular form by treatment received (RZL-012 / placebo) by cohort and overall.

The average change in Face Q questionnaires score from baseline will be presented in a tabular form by treatment received (RZL-012 / placebo) by cohort and overall.

Any statistical tests will be two-sided. The required significance level (p value) of findings will be equal to or lower than 5%.

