10.5.5. Efficacy Analysis

The change from baseline of submental fat volume will be presented in tabular form by treatment and dose.

The changes from baseline in FACE-Q score as a function of treatment group will be presented in tabular form per treatment group and dosing group.

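### FACE-Q is planned only as unadjusted change by arm; a baseline-adjusted active-minus-placebo difference with a confidence interval would use data already being collected

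*Combined protocol and SAP*

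**What the plan says.** The FACE-Q endpoint (Section 4.2, item 3; Section 10.2.2) is improvement from baseline at Days 28, 56 and 84, RZL-012 against placebo. Section 10.1 introduces the secondary endpoints with "Secondary endpoints will test the efficacy of RZL-012 vs. placebo according to the following measures". Section 6.1.10 and Appendix I schedule a FACE-Q score before injection for every subject.

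The analysis text stops at summaries by arm. Section 10.5.1 calls the analyses mainly descriptive, with data "tabulated and summarized using the mean, standard deviation or standard error". For FACE-Q it says "The average change in Face Q questionnaires score from baseline will be presented in a tabular form by treatment received", by cohort and overall. Section 10.5.5 repeats the idea: "The changes from baseline in FACE-Q score as a function of treatment group will be presented in tabular form". Neither section names an active-minus-placebo difference, an interval, a model or a covariate.

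MRI volume is handled the same way: "The average change from baseline in submental volume as analyzed from MRI images will be presented in a tabular form by treatment received" (10.5.1) and "The change from baseline of submental fat volume will be presented in tabular form by treatment and dose" (10.5.5). No section says outright whether that change is absolute or percent.

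**The concern.** The quantity the endpoint asks about is the difference between arms. A table of arm means leaves the reader to form that difference and its uncertainty. With 4 placebo subjects in cohort 1 and at least 4 in cohort 2, chance imbalance in starting FACE-Q scores is to be expected.

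Raw change stays unbiased over repeated randomisations. But it fixes the coefficient on baseline at 1, and when the true slope is lower this adds noise. What is at stake is precision: in a study of 28 subjects, the FACE-Q comparison may carry a wider interval than the same data allow.

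**Working it through.** **No plan figure to reproduce.** Section 10.3 bases the 12 + 16 subjects on discussions with physicians and on the literature. It gives no power, effect size or SD.

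**Inputs.** Cohort 1 is 8 active and 4 placebo (Section 3.1). Cohort 2 is 16 with at least 4 placebo (Section 10.3), taken here as 12:4. The correlation rho between baseline and follow-up FACE-Q is not given and is varied from 0.3 to 0.9.

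**Closed form.** Assume equal SD s at both times, and write m = 1/n1 + 1/n2.

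- Raw change: variance of the difference = 2s²(1 − rho)m.
- Baseline-adjusted: variance = s²(1 − rho²)m × [1 + 1/(n − k − 2)], where k counts the parameters other than baseline. The bracket is the cost of estimating the slope.
- CI-width ratio, adjusted to raw = √{(1 + rho)/2 × [1 + 1/(n − k − 2)]} × t(n − k − 1)/t(n − k).

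Pooled model with treatment and cohort: n = 28, k = 3, bracket = 1 + 1/23 = 1.043, t ratio = 2.064/2.060. At rho 0.5: √(0.75 × 1.043) × 1.002 = 0.89. Adding treatment-by-cohort (k = 4, bracket 1 + 1/22 = 1.045, t 2.069/2.064) changes the ratio by about 0.001.

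The ratio reaches 1 at rho = 2/[bracket × (t ratio)²] − 1:

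- pooled, 0.91;
- shared-slope model with treatment-by-cohort, 0.90;
- cohort 2 fitted alone (n = 16, k = 2), 0.82;
- cohort 1 fitted alone (n = 12, k = 2), 0.72.

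This is why one shared-slope model is better than two separate fits.

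**Through the actual scoring.** The closed form ignores the 0–100 bounds and the uneven conversion in Appendix III, so trials were simulated. Assumptions: 8:4 plus 12:4; sum scores with SD 5; placebo shift 2; true gain 5 over placebo; scores rounded, limited to 10–40 and converted. There were 20,000 trials per setting for baseline means 18 and 22 (type I error 4.7–5.2%), and a smaller run of 6,000 for mean 26.

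| CI-width ratio, adjusted/raw | rho 0.3 | 0.5 | 0.7 | 0.9 |
|---|---|---|---|---|
| Closed form, pooled | 0.83 | 0.89 | 0.94 | 1.00 |
| Simulated, baseline sum-score mean 18 | 0.81 | 0.86 | 0.91 | 0.95 |
| Simulated, mean 22 | 0.89 | 0.95 | 1.00 | 1.00 |
| Simulated, mean 26 | 0.89 | 0.95 | 1.00 | 1.01 |

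In FACE-Q points at rho 0.5, the mean pooled half-width goes from 10.8 to 9.3 (mean 18) or from 11.1 to 10.5 (mean 22). The gain therefore depends on where subjects start. With mean 22 it ends near rho 0.7, well below the closed-form 0.91.

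**Separating the sources of gain.** Take the cohort 1 dose at rho 0.5, where the SD of change equals s and m = 1/8 + 1/4 = 0.375.

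- Raw change, cohort 1 alone: t(10) = 2.228, half-width 2.228 × √0.375 = 1.36 s.
- Raw change in one model for both cohorts: t(24) = 2.064, 2.064 × √0.375 = 1.26 s.
- Baseline added: 1.26 × 0.89 = 1.12 s.

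Only the last step, 1.26 to 1.12, comes from the baseline score. The interval stays wide either way.

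**Why a cohort term.** At 12:4, cohort 2 supplies 12/20 = 60% of active but 4/8 = 50% of placebo subjects. A plain overall difference therefore carries 10% of any between-cohort difference. At 11:5 it is 11/19 − 5/9, about 2%.

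**The case against.** The strongest reply is that this is preference. Safety is the only primary objective, the analyses are declared mainly descriptive, and the sample size has no power target. Tables of means with SD or SE fit that design, and a reader can derive the unadjusted difference and its interval from means, SDs and numbers per arm. All of that stands, and it is why no error is alleged. What it does not answer is that the adjusted difference cannot be recovered from change tables by arm; it needs the subject-level relation between baseline and follow-up. A difference with an interval is itself a descriptive result.

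Several stronger readings are tempting, and the documents do not support them:

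- **The uneven conversion table shows that change depends on the starting score.** One step from sum score 10 moves 13 points and mid-scale steps move 1 to 3. But Appendix III is a Rasch transformation, and uneven steps per sum-score point are how such a scale works. In the simulation the scoring reduces the gain at means 22 and 26.
- **Adjustment lifts power from 43% to 61%.** That is the most favourable simulated setting (mean 18, rho 0.3). With mean 22 and rho 0.7 it is 83% against 84%.
- **The MRI scale is left open to choice after the data are seen.** The plain reading of change in volume is a volume difference. The percentages in Section 1.2.4.1.2 are of an injected-to-non-injected side ratio, a different quantity. In simulation neither scale was uniformly better: percent change did better under proportional measurement noise, absolute change under additive noise. A clarifying line is enough.
- **Twenty-one efficacy tests inflate the error rate to 66%.** The count (3 + 1 + 3 endpoint-visits × 3 groupings) is of possible comparisons; the plan only sets a level for any tests that are done. The figure 1 − 0.95^21 also assumes independence, which cannot hold when the overall comparison contains both cohorts.

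A fair caution also stands: one pooled effect would mix maximal doses of 120 mg and 240 mg and two vehicle volumes. The dose-specific estimates should come first.

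**Conclusion.** The point holds as a recommended improvement to a secondary, descriptive analysis. The plan gives no treatment difference or interval for FACE-Q and leaves the scheduled baseline score unused as a covariate.

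Under the assumed values, adjustment narrows the interval by 11 to 19% at rho 0.3, by 5 to 14% at rho 0.5 and by 0 to 9% at rho 0.7. At rho 0.9 the result runs from 5% narrower to 1% wider. These figures rest on assumed correlation, baseline mean, SD, effect size and a 12:4 split in cohort 2, none of which the documents supply.

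A reader might infer that the planned analysis is biased or would mislead. It is not biased on average, and the documents do not support that reading. The baseline argument does not extend to the physician's global assessment, which has no baseline score (Section 6.1.11).

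**What to change.** Keep the raw tables. Add to Section 10.5.5:

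1. FACE-Q active-minus-placebo difference with 95% CI at Days 28, 56 and 84, from one linear model per visit with treatment, cohort, treatment-by-cohort and baseline FACE-Q (one slope shared by both cohorts). Report the dose-specific differences first. Report the cohort-adjusted overall difference second, stating in advance how the two cohorts are weighted.
2. Minor wording: report the Day 84 MRI change as a cohort-adjusted treatment difference with 95% CI, and state whether the change is absolute or percent.
3. Minor wording: label any efficacy p-values exploratory.

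The change is to analysis text only, with no new visits, subjects or measurements. It costs one degree of freedom and the assumption that the baseline relation is the same in both cohorts. If the correlation turns out very high, the adjusted interval may be no narrower, or about 1% wider in the least favourable setting examined.

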10.5.2. Subject Disposition

A detailed description of subject accountability including count of subjects included, exposed, completed (i.e., subjects who complete the study treatment) and discontinued along with the main reason for discontinuation will be generated for each treatment group and for all subjects. All withdrawals from the study, taking place on or after study drug injection, will be fully documented in the body of the Clinical Study Report.

Note that the actual study duration is for a period of maximum 4.5 months, with efficacy analyses being conducted at Day 28, 56, and 84 visits.

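### Section 10.5.1 lets any two-sided p≤5% count as a finding across up to 21 unranked efficacy comparisons, with no key comparison and no multiplicity control

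*Combined protocol and SAP*

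**What the plan says.** Section 10.5.1 opens with "Statistical analyses will be mainly descriptive in nature". It ends with a rule for testing: "Any statistical tests will be two-sided", and "The required significance level (p value) of findings will be equal to or lower than 5" percent. No test or model is named there or in 10.5.5.

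Section 10.2.2 treats efficacy as something to be tested: "Secondary efficacy endpoints include testing of RZL-012 vs. placebo according to the following measures". The measures in 10.1 and 10.2.2 are:

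- Physician's global assessment: "Improvement in Physician's global assessment questionnaire for treatment efficacy assessment at Day 28, 56, and 84 following injection".
- FACE-Q score, change from baseline on the same three days.
- MRI volume: "Reduction from baseline in submental fat volume as measured by MRI, in RZL-012 treated subjects vs. placebo treated subjects at Day 84 following injection".

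For the changes in MRI volume and FACE-Q, 10.5.1 says that results "will be presented in a tabular form by treatment received (RZL-012 / placebo) by cohort and overall". It gives the physician's assessment the same breakdown by cohort and overall. Section 10.5.2 adds a note on timing: "with efficacy analyses being conducted at Day 28, 56, and 84 visits".

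All three measures are secondary; the primary endpoint is safety (4.1, 10.2.1). No section ranks an efficacy endpoint, visit or comparison, adjusts for multiplicity, or calls the p-values nominal.

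**The concern.** A purely descriptive plan needs no threshold for findings, and a plan that tests needs to say which test decides. This one does neither. Under 10.5.1, a physician grade at Day 28 in cohort 1 that reaches p≤5% is as much a finding as the Day 84 MRI result.

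The results are not equally reliable. The physicians are unblinded (3.1, 6.2.2), whereas 6.1.9 and 6.1.15.2.2 present MRI volume as the plan's objective measure.

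At stake is how the efficacy results can be read. With many unranked comparisons, an inactive drug could be reported with a statistically significant benefit on one of them. The sponsor could not show afterwards that this result was the one meant to count.

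**Working it through.** **Plan's own figure.** There is none to reproduce. The documents give no family-wise error rate, power, effect size or SD. Section 10.3 bases the sample size on discussions with physicians and on the literature.

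**Inputs from the documents**

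- Level: two-sided 5% per test (10.5.1).
- Endpoint-visit results: physician's assessment 3, FACE-Q 3, MRI 1 (10.1, 10.2.2).
- Comparisons: cohort 1, cohort 2, overall (10.5.1).
- Cohort 1: 8 active, 4 placebo (3.1).
- Cohort 2: 16 subjects, at least 4 on placebo (10.3), taken as 12:4.
- Overall, by addition: 20:8.

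**Count.** (3 + 3 + 1) × 3 = 21 comparisons.

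**Expected false findings, all 21 tested, no drug effect.** 21 × 0.05 = 1.05 in either direction. Half favour RZL-012: 21 × 0.025 = 0.525.

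**Independence reference, k tests**

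- Either direction, 1 − 0.95^k: k = 7 gives 30.2%; k = 21 gives 65.9%.
- Favouring RZL-012, 1 − 0.975^k: k = 7 gives 16.2%; k = 21 gives 41.2%.

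The 21 tests cannot be independent, because the overall comparison reuses the cohort data. I therefore simulated it.

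**Simulation.** 200,000 null trials per setting, normal outcomes, two-sample t-tests at 8:4, 12:4 and 20:8, with the overall test run on the same subjects as the cohort tests. The documents give no correlations, so these are assumptions, shown as a range.

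| Within-endpoint / between-endpoint correlation | 21 tests, either direction | 21 tests, favouring RZL-012 | 7 overall tests, either direction | 7 overall tests, favouring RZL-012 |
|---|---|---|---|---|
| 0 / 0 | 58% | 35% | 30% | 16% |
| 0.5 / 0.2 | 53% | 29% | 27% | 14% |
| 0.7 / 0.3 | 48% | 26% | 24% | 12% |
| 0.8 / 0.5 | 42% | 22% | 20% | 10% |
| 0.9 / 0.7 | 34% | 17% | 16% | 8% |

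With cohort 2 at 11:5 instead of 12:4, the either-direction figure at 0.6 / 0.3 barely moves (about 50% for both).

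**Benchmark.** One pre-named two-sided test at 5% has a 2.5% chance of a false result favouring RZL-012. The 21-test figure is about 7 to 14 times that (17/2.5 to 35/2.5). The seven-test figure is about 3 to 6 times (8/2.5 to 16/2.5).

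**Power of a single key test.** For a t-test with standardised difference d, the noncentrality is d × √(n₁n₂/(n₁+n₂)).

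- 12 vs 4: √(48/16) = 1.732. With d = 1.74 the noncentrality is 3.01 on 14 degrees of freedom, and power is 80%.
- 20 vs 8: √(160/28) = 2.390. With d = 1.22 the noncentrality is 2.92 on 26 degrees of freedom, and power is 80%.

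**The case against.** The strongest reply is that this is a 28-subject Phase 2a study with a safety primary endpoint, that 10.5.1 calls the analysis mainly descriptive, and that its rule is conditional: it governs any tests that are run. Presentation by cohort and overall specifies tables, 10.5.5 prescribes only tables, and 10.5.2 mentions efficacy analyses in a note on timing.

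Much of this stands. The documents do not commit to 21 p-values, so 21 is an upper count. No confirmatory efficacy claim rests on a p-value, so this is not a failure of a confirmatory error rate. The reply does not remove the problem. Sections 10.1 and 10.2.2 do say that efficacy will be tested, 10.5.1 does define a finding, and the conditional wording leaves the choice of tests open until the data are seen.

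Three stronger readings are tempting, and the documents do not support them.

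- A reader might infer that a false efficacy finding is about as likely as not. That figure counts rejections in both directions; about half favour placebo and would not be reported as efficacy.
- A reader might quote the independence value of 65.9%. It ignores the overlap between the cohort and overall comparisons and any correlation among outcomes.
- A reader might discount Day 28 because edema and induration are still being graded then. They are graded at Day 84 as well (6.1.7, Table 4, Appendix I), so the grading schedule does not separate the two visits.

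**Conclusion.** The point holds as a defect in how efficacy p-values will be interpreted. The plan sets a 5% rule for findings over up to 21 comparisons, with none named as key and no multiplicity control.

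If all 21 were tested with an inactive drug, the chance of at least one false result favouring RZL-012 would be about 17–35%, and 22–29% at the moderate correlations. For the seven overall comparisons alone it would be about 8–16%.

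These figures assume no effect on any endpoint, t-tests on normal data, cohort 2 at 12:4, and assumed correlations (0 to 0.9 within an endpoint, 0 to 0.7 between endpoints). The physician's grade is ordinal, and with four placebo subjects per cohort its tests could be conservative, which would lower the rates somewhat. The change is worth making, but it bears on secondary results and does not touch the safety objective.

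**What to change.** In 10.5.1, replace the 5% sentence with a statement that efficacy results are reported as estimates with 95% confidence intervals, and that any p-values are nominal and exploratory and do not count as findings. This is enough to resolve the point.

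If the sponsor wants one test to count, name it before unblinded efficacy data are reviewed. An example is change in MRI submental fat volume at Day 84, RZL-012 versus placebo, either overall or in cohort 2. A cohort 2 comparison should be worded for the dose actually given, because 3.2 and 3.3.1 allow that cohort not to escalate. All other comparisons would stay nominal.

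The cost is text only: no new data, visits or subjects. The sponsor gives up calling secondary p-values significant. Any single key test would also have low power: 80% only for a true difference of about 1.74 SD at 12 versus 4, or 1.22 SD at 20 versus 8. That low power is a further reason to rely on estimates and intervals.
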